## 6.5 Withdrawal criteria

Subjects are free to withdraw from the study at any time, without prejudice to their continued care. Subjects who withdraw from the study should complete the PEOT Visit (see [Section 8.5](#)).

Subjects should be withdrawn from the study and will be encouraged to come back for the SFU Visit 20 weeks after final dose of IMP if the subject withdraws his/her consent or the Sponsor or a regulatory agency requests withdrawal of the subject.

A subject should be withdrawn from IMP and will be asked to come back for the SFU visit 20 weeks after final dose of IMP if any of the following events occur:

1. Subject develops an illness that in the opinion of the Investigator would interfere with his/her continued participation if the risk of continuing IMP outweighs the potential benefit.
2. Subject develops erythrodermic, guttate, or pustular form of PSO.
3. Subject is noncompliant with the study procedures or medications in the opinion of the Investigator.

4. Subject uses prohibited concomitant medications, with the exception of topicals, as defined in this protocol ([Section 7.8.2](#)), that may present a risk to the safety of the subject or the integrity of the study data, in the opinion of the Investigator and/or the Medical Monitor.
5. Subject has a clinical laboratory value meeting any of the following criteria:
  - a. Hepatotoxicity as described in [Section 6.5.1](#)
  - b. A laboratory value meeting any of the following criteria:
    - Absolute neutrophil count  $<1.0 \times 10^3/\mu\text{L}$
    - Absolute lymphocyte count  $<0.2 \times 10^3/\mu\text{L}$

Subjects may remain in the study if the result is transient. A retest is required within 1 to 2 weeks at a scheduled or unscheduled visit. If the repeat absolute neutrophil count or absolute lymphocyte count is still below the allowable values, the subject must be withdrawn. If the repeat absolute neutrophil count or absolute lymphocyte count is above the allowable values, the subject may continue in the study.

6. The subject experiences a severe AE, an SAE, or a clinically significant change in a laboratory value that, in the opinion of the Investigator, merits the discontinuation of the investigational product and appropriate measures being taken.
7. There is confirmation of a pregnancy during the study, as evidenced by a positive pregnancy test (see [Section 12.1.4](#) for more information regarding pregnancies).
- 8b. At Week 28 and all following visits, subjects on continuous treatment for at least 12 weeks with a persistent IGA score  $\geq 3$  over at least a 4-week period are defined as nonresponders and should discontinue IMP.
- 9a. A subject considered as having either a suspected new latent tuberculosis infection (LTBI) or who develops active TB or pulmonary NTMB infection during the study (including but not limited to, conversion demonstrated by IGRA or other diagnostic means) must be immediately discontinued from IMP.

The subject must be permanently withdrawn if further examinations result in a diagnosis of pulmonary NTMB, active TB, or if the subject is diagnosed with LTBI with no initiation of prophylactic treatment, prematurely discontinues prophylactic treatment, or, in the opinion of the Investigator or Sponsor, is noncompliant with prophylactic TB therapy.

Confirmed active TB is an SAE and must be captured on an SAE Report Form and provided to the Sponsor in accordance with SAE reporting requirements. As with all SAEs, periodic follow-up reports should be completed as per protocol requirements until such time as the TB infection resolves.

Additional information on TB policies is provided in [Section 12.3.1](#).

10. Subjects with newly diagnosed inflammatory bowel disease (IBD) or with IBD flares during the study must:
  - Be referred, as appropriate, to a health care professional treating IBD, such as a gastroenterologist
  - Discontinue IMP and be followed-up until resolution of active IBD symptoms

If IBD flares increase in severity or frequency during the study, the Investigator should use clinical judgement in deciding whether the subject should continue in the study and contact the Medical Monitor and UCB study physician to confirm the subject's suitability for continued participation in the study.

11a. Subjects **must be referred** immediately to a mental healthcare professional (eg, locally licensed psychiatrist, psychologist, or master's level therapist) and may be withdrawn from the study based upon the Investigator's judgment of benefit/risk for:

- Active suicidal ideation as indicated by a positive response (“Yes”) to Question 4 of the “Since Last Visit” version of the eC-SSRS.
- Moderately severe major depression as indicated by a PHQ-9 score of 15 to 19 if this represents an increase of 3 points compared to last visit.

12a. Subjects must be referred immediately to a mental healthcare professional (eg, locally licensed psychiatrist, psychologist, or master's level therapist) and must be withdrawn for:

- Active suicidal ideation as indicated by a positive response (“Yes”) to Question 5 of the “Since Last Visit” version of the eC-SSRS
- Any suicidal behavior since last visit
- Severe major depression as indicated by a PHQ-9 score  $\geq 20$

The mental health consultation must be recorded in source documentation.

Investigators should attempt to obtain information on subjects in the case of withdrawal or discontinuation. For subjects considered as lost to follow-up, the Investigator should make an effort (at least 1 phone call and 1 written message to the subject), and document his/her effort (date and summary of the phone call and copy of the written message in the source documents), to complete the final evaluation. All results of these evaluations and observations, together with a narrative description of the reason(s) for removing the subject, must be recorded in the source documents. The electronic Case Report Form (eCRF) must document the primary reason for withdrawal or discontinuation.

Investigators should contact the Medical Monitor, whenever possible, to discuss the withdrawal of a subject in advance.

### 6.5.1 Potential drug-induced liver injury IMP discontinuation criteria

Subjects with potential drug-induced liver injury (PDILI) must be assessed to determine if IMP must be discontinued. In addition, all concomitant medications and herbal supplements that are not medically necessary should also be discontinued.

The PDILI criteria below require immediate and permanent discontinuation of IMP for subjects with either of the following:

- ALT or AST  $\geq 8$ xULN
- ALT or AST  $\geq 3$ xULN and coexisting total bilirubin  $\geq 2$ xULN

The PDILI criterion below requires immediate discontinuation of IMP for:

- Subjects with ALT or AST  $\geq 3 \times \text{ULN}$  who exhibit temporally associated symptoms of hepatitis or hypersensitivity. Hepatitis symptoms include fatigue, nausea, vomiting, right upper quadrant pain or tenderness. Hypersensitivity symptoms include fever (without clear alternative cause), rash, or eosinophilia (ie,  $>5\%$ ).

If a nondrug-related cause for the symptoms can be confirmed, these subjects may resume IMP administration after discussion with the responsible UCB physician, but only when the requirements for rechallenge with IMP as provided in [Section 12.2.1.2.1](#) are followed.

The PDILI criterion below allows for subjects to continue on IMP at the discretion of the Investigator.

- Subjects with ALT or AST  $\geq 5 \times \text{ULN}$  and  $< 8 \times \text{ULN}$ , total bilirubin  $< 2 \times \text{ULN}$ , and no eosinophilia (ie,  $\leq 5\%$ ), with no fever, rash, or symptoms of hepatitis (eg, fatigue, nausea, vomiting, right upper quadrant pain or tenderness).

Evaluation of PDILI must be initiated as described in [Section 12.2.1](#) with repeat tests performed in two weeks. Upon re-test, if ALT or AST values have reduced to  $< 5 \times \text{ULN}$ , the subject can continue with the study. However, if ALT or AST remains  $\geq 5 \times \text{ULN}$  and  $< 8 \times \text{ULN}$  after re-test, IMP should be temporarily withheld and subject should undergo a repeat test in two weeks. If ALT or AST values remain  $\geq 5 \times \text{ULN}$  even after the second re-test, then the subject should be permanently withdrawn from the study and should be followed for possible drug-induced liver injury.

If subjects are unable to comply with the applicable monitoring schedule, IMP must be discontinued immediately.

Investigators should attempt to obtain information on subjects in the case of IMP discontinuation to complete the final evaluation. Subjects with PDILI should not be withdrawn from the study until investigation and monitoring are complete. All results of these evaluations and observations, as well as the reason(s) for IMP discontinuation and subject withdrawal (if applicable), must be recorded in the source documents. The eCRF must document the primary reason for IMP discontinuation.

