When IMP is stopped due to PDILI (as described in Section 6.5.1), IMP must be permanently discontinued unless a subsequent alternative diagnosis fully explains the hepatic findings. If a subsequent alternative diagnosis fully explains the hepatic findings, and the requirements provided in Section 12.2.1.2.1 are met, rechallenge with IMP may be appropriate.

Table 12-3 summarizes the approach to investigate PDILI.

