**Table 12-3: Required investigations and follow up for PDILI**

| Laboratory value  |                     | Symptoms a of hepatitis or hypersensitivity |     | Immediate  |   | Follow up   |  |
|-------------------|---------------------|--|-----|--|---|---|--|
| ALT or AST        | Total bilirubin     | NA   | Yes | Consultation requirements  | Actions   | Testing   | Evaluation   |
| ≥3xULN            | ≥2xULN b | NA   | Yes | Hepatology consult c
Medical Monitor must be notified within 24 hours (eg, by laboratory alert) and subject discussed with Medical Monitor ASAP.     | Immediate, permanent IMP discontinuation. e  | Essential: Must have repeat liver chemistry values and additional testing completed ASAP (see Section 12.2.1.3); recommended to occur at the site with HCP.               | Monitoring of liver chemistry values at least twice per week until values normalize, stabilize, or return to within baseline values. d  |
| ≥8xULN            | NA                  | NA   | NA  | Hepatology consult.
Medical Monitor must be notified within 24 hours (eg, by laboratory alert) and subject discussed with Medical Monitor ASAP.                 | Immediate, permanent IMP discontinuation.   |   |  |
| ≥5xULN and <8xULN | <2xULN              | No   | No  | Discussion with Medical Monitor required.
Consider need for hepatology consult if there is no evidence of resolution (see Follow up requirements). e | Further investigation – immediate IMP discontinuation not required (see Section 12.2.1.2).

IMP discontinuation required if any of the following occur:
Subject cannot comply with monitoring schedule.
Liver chemistry values continue to increase
Liver chemistry values remain ≥5xULN after | Essential: Every attempt must be made to have repeat liver chemistry values and additional testing completed within 48 hours at the site with HCP (see Section 12.2.1.3). | Monitoring of liver chemistry values at least twice per week for 2 weeks. d 
 
Immediate IMP discontinuation required if liver chemistry values continue to increase.
 
 After 2 weeks of monitoring liver chemistry values: 
 
ALT or AST remains ≥5xULN <8xULN, IMP should be temporarily withheld and subject should undergo repeat test in 2 weeks.
 
 |

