#### 12.2.1.2.1 IMP restart/rechallenge

Subjects who are immediately discontinued from IMP due to having met certain criteria for PDILI (as described in [Section 6.5.1](#) and [Table 12-3](#)), but for whom an alternative diagnosis is confirmed, ie, drug-induced liver injury is excluded, can rarely restart IMP.

Rechallenge with IMP can occur only if ALL of the following requirements are met at the time of the rechallenge.

- The results of additional testing and monitoring described in [Section 12.2.1.3](#) and [Section 12.2.1.4](#) confirm a nondrug-related cause for the abnormal hepatic laboratory parameters and any associated symptoms (ie, a subsequent alternative diagnosis fully explains the hepatic findings).
- The subject has shown clear therapeutic benefit from the IMP.
- Subject's ALT or AST elevations do not exceed  $\geq 5xULN$ .
- Subject's total bilirubin is  $< 2xULN$ .
- Subject has no signs or symptoms of hypersensitivity or hepatitis.
- During the double-blind Treatment Period, the rechallenge is approved by the UCB responsible physician, DMC, and a hepatologist.
- During the OLE and OLE2 Periods, the rechallenge is approved by the UCB responsible physician.
- Subject agrees to the Investigator-recommended monitoring plan.

---

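### Section 6.5.1 makes the treatment stop permanent without exception for the two most severe liver classes, but Section 12.2.1 lets the same stops be followed by rechallenge, and Section 12.2.1.2.1 does not say which classes it covers

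*Protocol*

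**What the plan says.** Section 6.5.1 defines three classes in which IMP is stopped at once. For two of them, ALT or AST ≥8xULN and ALT or AST ≥3xULN with total bilirubin ≥2xULN, the lead-in is "The PDILI criteria below require immediate and permanent discontinuation of IMP for subjects with either of the following", and no exception follows. The third class, ALT or AST ≥3xULN with symptoms of hepatitis or hypersensitivity, is also stopped at once, but the word permanent is absent. If a non-drug cause is confirmed, "these subjects may resume IMP administration after discussion with the responsible UCB physician, but only when the requirements for rechallenge with IMP" in Section 12.2.1.2.1 are followed.

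Section 12.2.1 draws no such line: "When IMP is stopped due to PDILI (as described in Section 6.5.1), IMP must be permanently discontinued unless a subsequent alternative diagnosis fully explains" the findings. If it does, and the "requirements provided in Section 12.2.1.2.1 are met, rechallenge with IMP may be appropriate".

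Table 12-3 gives "Immediate, permanent IMP discontinuation" as the action for ≥8xULN, with no footnote. The same action for the ≥3xULN entries carries footnote e, which points to Section 12.2.1.2.1.

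Section 12.2.1.2.1 says that restart is rare. It requires a confirmed alternative diagnosis and a full list of conditions judged when treatment is resumed. In the double-blind period the sponsor's physician, the DMC and a hepatologist must approve. Later, "During the OLE and OLE2 Periods, the rechallenge is approved by the UCB responsible physician".

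For subjects at ≥5xULN and <8xULN without symptoms, Section 6.5.1 says that if values are still ≥5xULN after the second re-test the subject is to be withdrawn from the study and followed. The section then closes with "Subjects with PDILI should not be withdrawn from the study until investigation and monitoring are complete".

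**The concern.** A stopping rule for the most serious liver events should give one answer per laboratory class. Here the section that sets the rule and the section that sets the follow-up differ on whether a permanent stop admits an exception. The section that should settle the matter limits itself to an unnamed part of the criteria.

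The classes affected matter for safety. The bilirubin class contains the cases that Section 12.1.1.3 treats as potential Hy's Law, an adverse event of special interest, and Section 12.1.1.4 lists liver enzyme changes as a safety topic of interest. Exposure after such an event could depend on which section was taken to govern.

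Review is also thinnest where the ambiguity lasts longest. Section 12.4.4 ends DMC monitoring with the last Week 48 visit, or the safety follow-up visit for subjects who do not enter the extension. In the OLE and OLE2 periods, where dosing continues as late as OLE2 Week 40, the sponsor's physician is the only approver listed for rechallenge.

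**Working it through.** No sample-size, power or alpha figure bears on this point, so the check sets the texts side by side.

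| Class | Section 6.5.1 | Section 12.2.1 | Table 12-3 |
|---|---|---|---|
| ALT/AST ≥8xULN | Permanent, no exception | Permanent unless another diagnosis explains it; rechallenge then possible | Permanent, no pointer to rechallenge |
| ALT/AST ≥3xULN with bilirubin ≥2xULN | Permanent, no exception | As above | Permanent, with footnote e to rechallenge |
| ALT/AST ≥3xULN with symptoms | Immediate stop; may resume under conditions | As above | Apparently permanent, with the same footnote e |

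1. **Section 6.5.1 against Section 12.2.1.** Section 12.2.1 cites 6.5.1 as a whole, so its exception reaches both classes that 6.5.1 closes. That gives two firm conflicts.

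2. **Section 6.5.1 against Table 12-3.** For ≥8xULN the two agree, so the table is at odds with 12.2.1 instead. For the bilirubin class, footnote e suggests that rechallenge is possible. This is weaker evidence, because the bilirubin and symptom rows are run together in the text available. The copy of the table in the Amendment 2 log prints them as two rows with the second action cell empty, which is consistent with one shared cell. The footnote may therefore be meant for the symptom class, which 6.5.1 itself sends to 12.2.1.2.1.

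3. **Count.** Two closed classes times two comparison texts make four pairings. Two are firm conflicts (12.2.1, both classes), one is a weak conflict (Table 12-3, bilirubin), and one agrees (Table 12-3, ≥8xULN).

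4. **Does Section 12.2.1.2.1 settle it?** No. It points back to 6.5.1 and Table 12-3 without naming a class. Its ALT/AST and bilirubin limits apply at the time of rechallenge, so an earlier peak of ≥8xULN, or an earlier bilirubin ≥2xULN, is not itself a bar. The conditions exclude neither closed class.

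5. **Subjects still ≥5xULN after the second re-test.** The body of 6.5.1 says withdrawn from the study and followed. Table 12-3 says permanent IMP discontinuation with continued monitoring. The end of 6.5.1 says no study withdrawal until investigation and monitoring are complete. All three provide for follow-up; they differ on whether the subject leaves the treatment or the study.

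**The case against.** The strongest reply is that 12.2.1 is the follow-up section to 6.5.1, names it, and simply adds an exception to a general rule. That is a plausible reading, but it leaves two things unexplained. The separate resumption clause that 6.5.1 gives to the symptom class alone would have no function, and the ≥8xULN row of Table 12-3 would still lack the pointer to rechallenge.

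The rest of the reply limits the size of the point, and it stands:

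- A reader might infer that Table 12-3 also opens ≥8xULN to rechallenge. It does not, because that row carries no footnote.
- A reader might infer that a site can re-dose on its own reading once it proposes another cause. The protocol asks for a confirmed diagnosis that fully explains the findings, exclusion of drug-induced injury, every listed condition and the sponsor's physician's approval. In the double-blind period the DMC and a hepatologist must approve as well.
- A reader might infer that subjects still ≥5xULN after the second re-test lose their liver monitoring. The sentence in 6.5.1 that withdraws them also requires follow-up, its closing text defers study withdrawal, and Section 12.2.1.4 continues monitoring until values normalise, stabilise or return to baseline.

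**Conclusion.** The contradiction is real but narrow. Two of the three stop classes in Section 6.5.1 have a different final outcome in Section 12.2.1, and Section 12.2.1.2.1 does not decide between them. This rests on the plain text of 6.5.1 and 12.2.1 and does not depend on where footnote e sits in Table 12-3.

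The immediate action is not in doubt: 6.5.1 and Table 12-3 both require the drug to be stopped at once for both severe classes. The outcomes part only later, in the rare case where a non-drug cause is confirmed, all conditions are met and approval is given. Few subjects are likely to be affected, although the protocol gives no expected count, and no effect on sample size, power or alpha was identified. It would go too far to say that one liver event may freely end in either a lifelong stop or re-dosing. The documents speak of a permanent stop and place strict conditions on restart.

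The study-or-treatment wording for values still ≥5xULN after the second re-test is a lesser inconsistency of the same kind.

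**What to change.** Reconcile Section 6.5.1, Section 12.2.1, Section 12.2.1.2.1 and Table 12-3:

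- State one final outcome for each laboratory class and use it in all four places.
- In Section 12.2.1.2.1, name the classes to which rechallenge applies.
- Place footnote e in Table 12-3 only on those classes, with the bilirubin and symptom rows clearly separated.
- For values still ≥5xULN after the second re-test, say in 6.5.1 and Table 12-3 alike whether the subject leaves the treatment or the study, consistent with the closing text of 6.5.1.

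Which classes allow rechallenge is a clinical decision for the sponsor, and this review takes no position on it. The cost is a protocol clarification letter or a text-only amendment, with no new procedures or data.

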**Table 12-3: Required investigations and follow up for PDILI**

| Laboratory value |                 | Immediate  |                           | Follow up  |         |  |
|------------------|-----------------|--|---------------------------|--|---------|--|
| ALT or AST       | Total bilirubin | Symptoms a of hepatitis or hypersensitivity | Consultation requirements | Actions  | Testing | Evaluation   |
|                  |                 |  |                           | 4 weeks of monitoring without evidence of resolution |         | Continue IMP if ALT or AST values <5xULN; continue to monitor at least twice per week until values normalize, stabilize, or return to within Baseline values.
If ALT or AST remains ≥5xULN after second re-test, immediate, permanent IMP discontinuation required.

Continue to monitor until values normalize, stabilize, or return to within baseline values. d |

ALP=alkaline phosphatase; ALT=alanine aminotransferase; ASAP=as soon as possible; AST=aspartate aminotransferase; HCP=healthcare practitioner; IMP=investigational medicinal product; NA=not applicable; PDILI=potential drug-induced liver injury; ULN=upper limit of normal

a Hepatitis symptoms include fatigue, nausea, vomiting, and right upper quadrant pain or tenderness; hypersensitivity symptoms include eosinophilia (>5%), rash, and fever (without clear alternative cause)

b If the subject also has ≥2xULN ALP, the possibility of an indication of biliary obstruction should be discussed with the Medical Monitor.

c Details provided in Section 12.2.1.1. The local hepatologist is the expert usually consulted by the treating physician for assessment and management of potential hepatic disease. This would usually be a hepatologist, but may be a gastroenterologist.

d Unless an alternative monitoring schedule is agreed by the Investigator and UCB responsible physician. Determination of stabilization is at the discretion of the Investigator in consultation with the hepatologist (as applicable) and UCB responsible physician, as needed.

e Details provided in Section 12.2.1.2.1.

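### For ALT/AST still at or above 5×ULN after the second re-test, the protocol is inconsistent on whether study participation or IMP ends, and when

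*Protocol*

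**What the plan says.** Section 6.5.1 covers subjects with ALT or AST from 5×ULN to below 8×ULN, total bilirubin below 2×ULN, and no eosinophilia, fever, rash or hepatitis symptoms. Evaluation starts "with repeat tests performed in two weeks". If values are still in that band, "IMP should be temporarily withheld and subject should undergo a repeat test in two weeks". If they are at 5×ULN or above even after this second re-test, "then the subject should be permanently withdrawn from the study and should be followed for possible drug-induced liver injury".

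The closing paragraph of Section 6.5.1 adds: "Subjects with PDILI should not be withdrawn from the study until investigation and monitoring are complete". It asks for the reasons for IMP discontinuation and, where it applies, for subject withdrawal, as separate items.

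Table 12-3 introduces its action list for the same laboratory row with "IMP discontinuation required if any of the following occur". For the second re-test it states: "If ALT or AST remains ≥5xULN after second re-test, immediate, permanent IMP discontinuation required". The next instruction is "Continue to monitor until values normalize, stabilize, or return to within baseline values". The table does not mention study participation.

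Section 6.5 keeps two lists. Study withdrawal is for withdrawn consent or a request from the sponsor or a regulator. A separate list covers withdrawal from IMP with return for the safety follow-up (SFU) visit, and hepatotoxicity (criterion 5a, which refers to Section 6.5.1) is in that second list.

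**The concern.** A site facing this result needs to know two things: whether the subject leaves the study or stops IMP, and whether that happens before or after the liver work-up is finished. The current text gives more than one answer to each.

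Two things are at stake. The first is disposition. TEAEs leading to withdrawal are a secondary safety variable (Section 4.2.2), and Section 14.5.1 plans a table of AEs leading to withdrawal from the study. If one site records study withdrawal and another records IMP discontinuation for the same event, such counts depend partly on how the site read the rule. The second is hepatic follow-up. Liver enzyme elevation is a pre-specified safety topic (Section 12.1.1.4), and a site could end participation while liver monitoring is still required.

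**Working it through.** No sample size, power or alpha enters. The check is textual, with one timing calculation.

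1. **Same event, same time?** In Section 6.5.1 the first re-test is at 2 weeks and the second 2 weeks later: 2 + 2 = 4 weeks. Table 12-3 requires IMP discontinuation if values are still at 5×ULN or above after 4 weeks of monitoring without evidence of resolution. Section and table therefore address the same subject at the same point.

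2. **Side by side.**

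| Place | Study participation | IMP | Liver monitoring |
|---|---|---|---|
| 6.5.1, second re-test sentence | Ends permanently; no date given | Permanent stop not stated | Follow-up for liver injury asked for |
| 6.5.1, closing paragraph | Not to end yet | Reason for stopping to be recorded | Must be complete first |
| Table 12-3, second re-test | Not mentioned | Stops at once, permanently | Continues |
| 6.5, criterion 5a | Not in the study-withdrawal list | Withdrawn, with SFU visit | Not addressed |

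3. **Is monitoring complete when the second re-test result arrives?** No. Values are still at 5×ULN or above, the second re-test sentence itself asks for follow-up, and Table 12-3 and Section 12.2.1.4 both continue monitoring until values normalize, stabilize or return to baseline. If the subject leaves the study when the second re-test result arrives, the closing paragraph's condition is not met.

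4. **Could the two terms mean the same thing?** Section 6.5 gives them different triggers, and the closing paragraph of Section 6.5.1 names both separately. Usage is not strict, however: criterion 5b, in the IMP list, speaks of subjects remaining in the study. A site cannot settle from the text alone which meaning applies.

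5. **Effect on the primary analysis.** Section 14.3.1 counts as a nonresponder anyone who withdraws from IMP before Week 16 or lacks Week 16 data. A permanent IMP stop or study withdrawal before Week 16 gives the same imputed result.

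6. **What liver follow-up remains after study withdrawal?** Sections 5.2.6 and 8.5 provide a premature end-of-treatment visit with the Week 48, Week 144 or OLE2 Week 48 assessments. Each includes biochemistry (Sections 8.2.13, 8.3.8, 8.4.5). The SFU visit also includes it (Sections 8.6, 8.7). Section 12.2.1 makes every such liver event a reportable AE, and Section 12.1.3 requires AEs to be followed until resolved, stable, no longer clinically significant or lost to follow-up.

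**The case against.** The strongest reply is that the two statements in Section 6.5.1 can be read in sequence. The second re-test sentence sets no date for leaving the study, and elsewhere the section says so when it means at once. On this reading the sentence gives the eventual disposition and the closing paragraph its earliest date. This is a fair reading and it softens the conflict within Section 6.5.1. It does not explain why the section speaks of the study where Table 12-3 and the heading over criterion 5a speak of IMP. It also leaves the site to infer the order.

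A second reply is that Table 12-3 is only silent on study participation, so stopping IMP is compatible with later study withdrawal. That is correct: the table should not be read as an instruction to keep the subject in the study. The silence still leaves disposition unsettled.

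A reader might infer that study withdrawal removes all scheduled liver tests except the 20-week safety visit, or that outcome data are bound to be lost. The documents do not support this, given the follow-up duties and the end-of-treatment biochemistry listed in the check. Nor does Table 12-3 set a twice-weekly schedule after a failed second re-test. It states that frequency for the first 2 weeks and for subjects who fall below 5×ULN, and a footnote allows an agreed alternative schedule. It would also be too strong to say that the section orders withdrawal and then forbids it, since the wording is should and should not.

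Finally, the eCRF and its guidelines are not at hand, so divergent recording between sites is possible but cannot be shown.

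**Conclusion.** The inconsistency is real and stands in the current text, not only in the amendment history. For one laboratory event, the protocol does not settle whether IMP or study participation ends, or when this happens relative to completion of liver monitoring. The consequence is a risk of inconsistent disposition and of participation ending while monitoring is still required. It is not a demonstrated loss of data.

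The rule reaches only subjects in the 5 to below 8×ULN band who meet the bilirubin and symptom conditions and stay at 5×ULN or above on two re-tests. The documents give no count. The primary analysis is essentially unaffected. The point merits correction because it concerns a liver-safety stopping rule that sites could apply differently, and because the correction is cheap. The conclusion rests on the protocol's own separation of study withdrawal from IMP withdrawal. No view is taken on which clinical rule is right.

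**What to change.** Reconcile Section 6.5 (heading over criterion 5a), both statements in Section 6.5.1 and the second re-test entry of Table 12-3 into one consistent statement. It should say whether IMP or study participation ends, and when, relative to completion of liver monitoring. Use the same term in all these places, and check that the disposition page of the eCRF uses it too.

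The cost is wording in two sections and one table, through the next amendment. No change to sample size or planned analyses follows.
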